- At least one Grade ≥ 3 Treatment-Related TEAE;
- At least one Serious TEAE;
- At least one Serious Treatment-Related TEAE;
- At least one TEAE leading to Discontinuation from Study Medication;

- At least one TEAE of Clinical Interest;
- At least one Treatment-Related TEAE of Clinical Interest

The incidence of all TEAEs by SOC and PT will be presented for the following:

- All TEAEs;
- Treatment-Related TEAEs;
- TEAEs with Grade ≥ 3 ;
- Serious TEAEs;
- Serious TEAEs with Grade ≥ 3 ;
- Treatment Related Serious TEAEs;
- TEAEs leading to Discontinuation from Study Treatment;
- Non-Serious TEAEs $\geq 5\%$ Threshold
- Non-fatal TEAEs
- Hypertension TEAEs by Pre-existing Hypertension (Yes vs No) and Baseline Hypertension (Yes vs. No). Hypertension TEAEs will be selected as any TEAE with Preferred Term of Hypertension.

Treatment listings will include the treatment arm, start and stop dates/times of the AE, and days on study relative to the day of first dose of study treatment.

A Treatment related AE is defined as an AE for which the investigator classifies the AE as being related to study treatment. To be conservative, the summary table will include events where the relationship to study treatment is missing. Missing severity for TEAEs will be counted as 'Severe'.

For the Non-Serious TEAEs $\geq 5\%$ Threshold, it will include adverse events if the event occurs at an incidence of greater than or equal to 5% in any treatment arm. No rounding is allowed. If an adverse event occurs at an incidence of 4.8%, for example, the incidence will not be rounded up to 5% for the purposes of this table.

Treatment Emergent Adverse Events of Clinical Interest (AECI) and Treatment-Related TEAEs of Clinical Interest will also be summarized by SOC and PT. Adverse Events of Clinical Interest for this study include:

- Potential Major Adverse Cardiac and Cerebrovascular Events (MACCE), which will be adjudicated by an independent external expert clinical adjudication committee (CAC) into the following categories according to the definitions in the CAC Charter:
 - Death or any event with fatal outcome
 - Myocardial infarction / Heart Attack
 - Cerebrovascular Accident / Stroke

- Hospitalization for Unstable Angina / Chest Pain
- Hospitalization for Heart Failure
- Coronary revascularization / Angioplasty / Stent
- Hypertension: An adverse event of hypertension should be reported and will be an AECI as follows:

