 - For patients without hypertension (average SBP <140 mmHg, DBP <90 mmHg) at baseline, at two consecutive visits, the average of three systolic blood pressure (SBP) \geq 140 mmHg or diastolic blood pressure (DBP) \geq 90 mmHg (or both); at 2 consecutive visits in patients who were not hypertensive at baseline; or,
 - For patients with hypertension at baseline, an increase compared to baseline at 2 consecutive visits in the average of three SBP by \geq 20 mmHg OR DBP by \geq 10 mmHg;
 - Initiation of, or increase in dose of, medication for treatment of hypertension in any patient.
- Adverse events consistent with orthostatic hypotension as confirmed by orthostatic vital signs.
- Adverse events suggestive of cystitis or urinary tract infection.
- Elevated AST or ALT lab value requiring that study drug be temporarily withheld or permanently discontinued (see [Section 8.6.1](#) and Section 8.6.2).

The following additional listings will be provided:

- Listing of deaths
- Listing of Serious TEAEs
- Listing of non-treatment-emergent SAEs
- Listing of TEAEs leading to withdrawal or temporary withdrawal of study treatment
- Listing of all AEs with a flag for TEAEs and onset (Prior = prior to first dose of single-blind medication, Run-in = on or after first dose of single-blind medication but prior to first dose of double-blind medication, or Treatment = on or after first dose of double-blind medication.)

A summary of all TEAEs by maximum intensity (mild, moderate, severe, life-threatening, death), SOC, and PT will be presented, where the maximum intensity per patient will be counted at each level of summarization. In addition, a summary of all TEAEs by relationship to study treatment (related, not related), SOC and PT will be presented, where all relationships to study treatment per patient will be counted at each level of summarization. A summary of all TEAEs by PT occurring in at least 2% of patients in the

vibegron arm and greater than the placebo arm will be created and sorted by descending frequency in the vibegron arm.

A listing of all Medical History and pre-double-blind treatment adverse events with coded preferred terms belonging to the standard MedDRA query of hypertension will be created.

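### The only hypertension TEAE table split by pre-existing and baseline hypertension counts a single Preferred Term, which is narrower than the other two definitions of hypertension in the same section

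*SAP*

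**What the plan says.** All the wording on event selection is in SAP Section 9.3 (Adverse Events), which identifies hypertension in three ways.

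- **Stratified TEAE table.** Among the incidence tables is one of hypertension TEAEs by Pre-existing Hypertension and by Baseline Hypertension. Its rule is "Hypertension TEAEs will be selected as any TEAE with Preferred Term of Hypertension".
- **Event of clinical interest.** The lead-in is "An adverse event of hypertension should be reported and will be an AECI as follows". For patients without hypertension at baseline, the trigger is an average SBP of at least 140 mmHg or DBP of at least 90 mmHg at two consecutive visits. For the others it is "For patients with hypertension at baseline, an increase compared to baseline at 2 consecutive visits in the average of three SBP by" at least 20 mmHg, or in DBP by at least 10 mmHg. A third trigger is "Initiation of, or increase in dose of, medication for treatment of hypertension in any patient".
- **History and pre-treatment listing.** Medical history and adverse events before double-blind treatment are listed if they have "coded preferred terms belonging to the standard MedDRA query of hypertension".

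The two strata are defined in Section 7.2. Baseline Hypertension is a baseline SBP of at least 140 mmHg or DBP of at least 90 mmHg. Pre-existing Hypertension is either that or a medical history of hypertension.

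The AECI output is described as follows: "Treatment Emergent Adverse Events of Clinical Interest (AECI) and Treatment-Related TEAEs of Clinical Interest will also be summarized by SOC and PT". Section 9.5 summarises blood pressure as continuous values and changes by visit.

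**The concern.** A standard MedDRA query is a set of terms, and the SAP itself speaks of Preferred Terms in the plural when it invokes the query. The plan therefore accepts that hypertension can be coded in more than one way. It uses that breadth for events before double-blind treatment and a single term for events on treatment. The same coded event could be picked up in the pre-treatment hypertension listing yet left out of the on-treatment hypertension table, and no reason is given.

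Hypertension is a named event of clinical interest, and its reporting criteria depend on whether the patient was hypertensive at baseline. The stratified table is where a reader would look to see whether events on vibegron arise mainly in patients with or without existing hypertension. If some events carry another term, that table is incomplete, and no other planned output is stated to show the missing events by stratum.

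**Working it through.** The SAP states no rate, count or precision for this table, so there is no figure to reproduce. The check sets the passages side by side.

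1. **What feeds the table.** Section 9.3 names one Preferred Term. It mentions no other term, term group or AECI flag as a source of events for this table.

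2. **What the wider definitions would admit.** The query admits any of its Preferred Terms. The AECI definition admits any event meeting a blood pressure or medication criterion and does not mention a Preferred Term. Each can include an event that the single-term rule excludes.

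3. **Where an excluded event still appears.**

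| Output (SAP section) | Event under another query term included? | Stated split by hypertension status? |
|---|---|---|
| Hypertension TEAE table (9.3) | No | Yes |
| All TEAEs by SOC and PT (9.3) | Yes | No |
| AECI summary by SOC and PT (9.3) | Yes, if it meets the criteria | No |
| Summaries by intensity and by relationship (9.3) | Yes | No |
| AE listing with onset flag (9.3) | Yes | No |
| Vital signs (9.5) | Readings, not events | No |

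   The omission is confined to the first row, which is also the only row with the split.

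4. **Size.** Let f be the share of on-treatment hypertension events coded to a term other than Hypertension. The table then shows the fraction 1 - f. The SAP gives no value for f; it can lie anywhere from 0 (nothing absent) to 1. With the same f in both strata, the counts shrink by the same factor and the ratio of incidences between strata is unchanged. Only an f that differs between strata would distort that ratio.

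5. **Effect on inference.** Section 9 plans no inferential testing of safety data, so neither type I error nor power is involved.

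**The case against.** The case for leaving the table alone has four parts.

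- **The AECI lead-in.** It tells sites to report an adverse event of hypertension when a criterion is met. The criteria are reporting instructions, and an event reported as instructed would naturally be coded to Hypertension. This stands as a reason to expect f to be small. It does not fix the coding, and it does not reach blood pressure events that fall short of the criteria.
- **Different purposes.** A wide net suits a listing of prior conditions, while a narrow, clearly labelled rule suits an event table. The rule is unambiguous and prespecified, and the query does not define the strata. This stands to the extent that the passages do not formally contradict each other. It does not explain why the one stratified output should use the narrowest of three definitions.
- **Nothing is lost from the report.** This is correct, as the table of outputs shows. The point concerns one table only.
- **Limited stakes.** Safety analysis is descriptive, and treatment is double-blind (Section 3.9), so the documents give no ground for expecting unequal loss between arms. This also stands.

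A reader might go further and infer that the shortfall is greatest in patients already hypertensive at baseline, on the argument that a further rise is less likely to be called hypertension. The documents do not support that. Section 9.3 has a reporting criterion written for exactly those patients, and the medication criterion applies to every patient. A reader might also want a percentage for the undercount, but the SAP contains neither a coding share nor an expected incidence from which to derive one.

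**Conclusion.** The point holds as a limited inconsistency in Section 9.3. The only table stated to be split by hypertension status selects events by one Preferred Term, while the same section uses a multi-term query and a criteria-based definition elsewhere. On-treatment events coded to other query terms would be absent from that split but present in the other planned outputs. The size is unknown and may be small.

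This rests on two assumptions: that at least some on-treatment events are coded to a query term other than Hypertension, and that no output outside the stated text makes the same split. A larger shortfall in patients hypertensive at baseline, or in one arm, is not established. Severity is low: a cheap improvement worth making before unblinding, so that the choice of terms cannot be questioned afterwards.

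**What to change.** In Section 9.3, change the selection rule for this table as follows:

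- select TEAEs whose Preferred Term is in the standard MedDRA query for hypertension, the query already used for the history listing, in the MedDRA version used for coding;
- show the Preferred Terms within each stratum, keeping Hypertension as its own row so that the count now planned is preserved;
- add a row for TEAEs flagged as AECIs in the hypertension category, because the query and the AECI criteria select different sets of events.

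The cost is a sentence or two in the SAP and a term lookup. No new data are needed. Some less specific terms will enter the table, but the row layout keeps them visible and separable.

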9.4. Laboratory Evaluations

Laboratory tests will be performed at Screening and periodically throughout the study as described in the Flowchart, [Section 3.11](#). Only data collected by the central laboratory will be included in the analyses and standard international units will be used for all summaries. Laboratory tests within each category and scheduled visit are given in [Table 9.4.1](#).

Table 9.4.1: Laboratory Tests and Scheduled Study Visits

Laboratory Category	Laboratory Tests Included (Central Lab)
Hematology	Hematocrit, Hemoglobin, Platelet Count, WBC (total and differential), RBC
Chemistry	Albumin, Alkaline Phosphatase, ALT, AST, Bicarbonate, Calcium, Chloride, Creatinine, Glucose (fasting and non-fasting), Potassium, Sodium, Total Bilirubin, Direct Bilirubin, BUN, Total Cholesterol, eGFR
Urinalysis	Blood, Glucose, Protein, Specific gravity, Microscopic exam (RBC, WBC, epithelial cells and bacteria), pH, Color, and Urine pregnancy test (β -hCG)
Other	Serum β -human chorionic gonadotropin (β -hCG), where applicable

a. A sample for urinalysis and urine culture will be sent to the central laboratory only if the urine dipstick performed at the site tests positive for the presence of leukocytes, nitrites, or blood cells.

b. Urine β -hCG will be tested for women of childbearing potential only. If urine β -hCG is positive, a serum β -hCG must be performed.

c. eGFR will be calculated and reported by the central lab.

d. If total bilirubin is elevated above the upper limit of normal.

Laboratory summaries will be based on the central laboratory data.

A sample for the urinalysis and urine culture will be sent to the central laboratory only if the urine dipstick performed at the site tests positive for the presence of leukocytes, nitrites, or blood cells.

Actual (observed) values and changes from baseline in hematology and chemistry laboratory parameters will be summarized by treatment group at each scheduled visit. The number and percentage of patients with laboratory measurements outside of the central laboratory normal range will also be summarized by treatment group and visit. Shift tables from baseline to maximum post-baseline value, to minimum post-baseline value, last post-baseline value, and at each post-baseline visit will be provided for hematology and chemistry parameters to display low, normal, high, and missing values by treatment group

in a 3-by-3 contingency table. Denominators for percentages will be the number of patients with non-missing data at the specific assessment and baseline.

Actual (observed) values in urinalysis and other laboratory parameters will be summarized by treatment group. The number and percentage of patients with laboratory measurements outside of the central laboratory normal range will also be summarized by treatment group and visit.

[figure not shown]
All data will be listed. Any data outside the central laboratory normal reference ranges will be explicitly noted on the listings that are produced.

[figure not shown]

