17. At Week 8, the Urine Dipstick will only be performed if clinically indicated (e.g., symptoms of urinary retention or urinary tract infection).

18. Urinalysis will be performed only if the urine dipstick tests positive for the presence of leukocytes, nitrites, or blood cells, and will be performed by the central lab.

19. Urine beta-human chorionic gonadotropin (β -hCG) will be tested for women of childbearing potential only.

Dosing/Drug

20. Dosing will occur every day from the Witnessed Dose on the day of the Run-in Visit through the day before the Week 12 Visit.

21. Study Treatment bottles should be returned by the patient at each visit. Clinic staff will perform accountability and review any discrepancies with the patient during the visit.

22. All patients will take their dose of Study Treatment on the day of the Run-in and Baseline Visits at the site as a witnessed dose. The date and time of Study Treatment dosing will be recorded

Pharmacokinetics Subset Only

23. PK samples for Population PK Analysis will be collected from a subset of patients (approximately 30% of enrolled patients) at selected sites. Pre-dose blood samples will be collected at Week 4, Week 8, and Week 12. PK samples should be collected during the clinic visit after all other study assessments have been completed.

24. The date and time of the last dose of Study Treatment prior to PK sampling will be recorded.

Follow-up/Unscheduled

25. Unscheduled Visits and the specific procedures performed at these visits will be determined by the Investigator, as clinically indicated. The procedures indicated in the Schedule of Activities will be performed at these visits, as clinically indicated, based on the purpose of the visit (e.g., follow-up for an adverse event or abnormal laboratory test, study treatment dispensation). The reason for the visit will be captured in the source documents.

26. For Patients who do not enroll into the optional extension study (RVT-901-3004) or patients who withdraw from the study for any reason, a Follow-up Visit should be performed approximately 28 days after the last dose of Study Treatment on Study Day 113 or approximately 28 days after a patient's Withdrawal from the study. When a patient withdraws from the study prior to study completion, all applicable activities scheduled for the Week 12 Visit should be performed at the time of withdrawal.

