12.2.5.2. Table Conventions

- Units will be included where available
- If the categories of a parameter are ordered, then all categories between the maximum and minimum category should be presented in the table, even if n=0 for all treatment groups in a given category that is between the minimum and maximum level for that parameter. For example, the frequency distribution for symptom severity would appear as:

Severity Rating	N
severe	0
moderate	8
mild	3

Where percentages are presented in these tables, zero percentages will not be presented and so any counts of 0 will be presented as 0 and not as 0 (0%).

- If the categories are not ordered (e.g., Medical History, Reasons for Discontinuation from the Study, etc.), then only those categories for which there is at least 1 patient represented in 1 or more groups should be included.
- An Unknown or Missing category should be added to any parameter for which information is not available for 1 or more patients.
- Unless otherwise specified, the estimated mean and median for a set of values should be printed out to 1 more significant digit than the original values, and standard deviations should be printed out to 2 more significant digits than the original values. The minimum and maximum should report the same significant digits as the original values. For example, for systolic blood pressure:

N	XX
Mean	XXX.X
Std Dev	X.XX
Median	XXX.X
Minimum	XXX
Maximum	XXX

- P-values should be output in the format: “0.xxx”, where xxx is the value rounded to 3 decimal places. Any p-value less than 0.001 will be presented as <0.001. If the p-value should be less than 0.0001 then present as <0.0001. If the p-value is returned as >0.999 then present as >0.999
- Percentage values should be printed to one decimal place, in parentheses with no spaces, one space after the count (e.g., 7 (12.8%), 13 (5.4%)). Pre-determine how to display values that round down to 0.0. A common convention is to display as '<0.1', or as appropriate with additional decimal places. Unless otherwise noted, for all percentages, the number of patients in the analysis set for the treatment group who have an observation will be the denominator. Percentages after zero counts should not be displayed and percentages equating to 100% should be presented as 100%, without any decimal places.

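### Urinalysis abnormality percentages in SAP 9.4 are conditional on a positive post-randomisation dipstick, so they overstate the population rate and can hide or dilute a difference between arms

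*SAP*

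**What the plan says.** **Who is tested.** The schedule in SAP Section 3.11 puts a urine dipstick at Screening, Baseline, Week 4, Week 12 and Follow-up. Footnote 17 makes one visit an exception: "At Week 8, the Urine Dipstick will only be performed if clinically indicated". Footnote 18 sets the condition for the next step: "Urinalysis will be performed only if the urine dipstick tests positive for the presence of leukocytes, nitrites, or blood cells". Section 9.4 repeats that condition and extends it to culture: "A sample for urinalysis and urine culture will be sent to the central laboratory only if the urine dipstick performed at the site tests positive".

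**What is tabulated.** For urinalysis, Section 9.4 says: "Actual (observed) values in urinalysis and other laboratory parameters will be summarized by treatment group". It then asks for the count and share of patients outside the central laboratory's normal range, per arm and visit. The same section restricts the source: "Only data collected by the central laboratory will be included in the analyses". No section of the SAP provides a table of site dipstick results.

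**Which denominator.** The urinalysis text in 9.4 names none. The one denominator sentence in that section follows the hematology and chemistry shift tables. The general rules therefore apply. Section 6.1 bases percentages on patients with non-missing data unless stated otherwise, and Section 12.2.5.2 says "the number of patients in the analysis set for the treatment group who have an observation will be the denominator". Section 5.4 adds that missing safety values are not imputed.

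**Urinary infection elsewhere.** Section 9.3 lists among the adverse events of clinical interest: "Adverse events suggestive of cystitis or urinary tract infection".

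**The concern.** A patient with a negative dipstick has no central urinalysis, so under the general rules that patient leaves the denominator and is not counted as free of an abnormality. What remains is a group selected on a result obtained after randomisation, and treatment may affect that result. The percentages by arm then no longer compare the groups as randomised.

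Two things follow. First, the printed percentages are far above the rate among all treated patients for findings that the dipstick screens for. Second, if one arm has more positive dipsticks, its numerator and denominator rise together and the percentage may hardly move. A reader who sees an imbalance in urinary infection adverse events and turns to the urinalysis table for an objective check could be wrongly reassured by near-equal percentages.

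**Working it through.** The SAP states no figure for dipstick positivity or urinalysis abnormality, so there is nothing to reproduce. The structure can be checked algebraically and illustrated with assumed rates.

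**Inputs**
- N = 500 in each of the vibegron and placebo arms (SAP 3.8).
- d = proportion with a positive dipstick. Assumed: 5% to 20% on placebo, and 1.5 to 3 times that on vibegron.
- a = proportion abnormal among the dipstick-positive. Assumed: 60% to 95%.

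**Formulas**
- Percentage under the SAP rule: (N × d × a) / (N × d) = a. The dipstick-positive rate cancels.
- Percentage of all patients in the arm: (N × d × a) / N = d × a.

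**Case 1: treatment changes only the dipstick-positive rate.** Take d = 10% on placebo and 20% on vibegron, with a = 80% in both.
- SAP rule: 40/50 = 80.0% versus 80/100 = 80.0%, difference 0.
- All patients: 40/500 = 8.0% versus 80/500 = 16.0%, difference 8.0 points.

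Over the whole assumed range, with a equal in the two arms, the SAP-rule difference is always 0. The all-patient difference runs from 1.5 points (3.0% versus 4.5%, at d = 5% and 7.5%, a = 60%) to 38 points (19.0% versus 57.0%, at d = 20% and 60%, a = 95%).

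**Case 2: mixed.** Assume a background dipstick-positive rate of 10% in both arms. Add infection in 2% on placebo and 6% on vibegron, every infected patient being both dipstick-positive and abnormal. The number with a result is 500 × 12% = 60 versus 500 × 16% = 80.

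| Background positives abnormal | SAP rule, placebo vs vibegron | Ratio | All patients, placebo vs vibegron | Ratio |
|---|---|---|---|---|
| 50% | 35/60 = 58.3% vs 55/80 = 68.8% | 1.18 | 7.0% vs 11.0% | 1.57 |
| 80% | 50/60 = 83.3% vs 70/80 = 87.5% | 1.05 | 10.0% vs 14.0% | 1.40 |
| 95% | 57.5/60 = 95.8% vs 77.5/80 = 96.9% | 1.01 | 11.5% vs 15.5% | 1.35 |

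The more often a positive dipstick is confirmed by the central result, the less of the difference the SAP percentage retains.

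**Check on the alternative denominator.** If the sentence after the shift tables in 9.4 were read as covering urinalysis too, a result would be needed at baseline as well. That would narrow the group to patients dipstick-positive on both occasions, a tighter selection still.

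**The case against.** A reader might infer that an effect on urinary infection would vanish from the laboratory tables, or from the trial. The SAP does not support that. Section 6.1 requires N, n and the frequency alongside the percentage, Section 12.2.4 puts N in the column heading, and Section 12.2.5.2 adds a missing category. In Case 1 the table would print 40 of n = 50 and 80 of n = 100, each under N = 500. Because a sample is sent only after a positive dipstick, n approximates the number dipstick-positive, apart from samples not sent or lost. A careful reader could recover the per-patient comparison. Urine culture is also sent, so urinalysis is not the only laboratory evidence. Cystitis and urinary tract infection events are summarised on the Safety Set without this selection.

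It can also be said that the denominator defaults yield to other specifications, and that Section 12.2.5.2 itself warns that denominators need care and sends details to footnotes. That leaves room for a correction, but 9.4 does not make one for the urinalysis panel that is run only after a positive screen.

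Two further limits stand. The exact zero in Case 1 comes from assuming the same a in both arms; Case 2 shows that some signal can survive. And safety data are descriptive (Section 9), so no type I error or power is involved.

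A blanket remedy that counts every dipstick-negative patient as normal would be wrong. The trigger covers leukocytes, nitrites and blood cells. It says nothing about glucose, protein, pH, specific gravity or color, which Table 9.4.1 also lists.

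**Conclusion.** The point holds for the percentages. Under the SAP's own rules the urinalysis abnormality percentage by arm and visit is conditional on a positive post-randomisation dipstick. For white cells, blood and bacteria it overstates the rate among all patients (80% against 8% and 16% in Case 1), provided dipstick-negative patients seldom have such findings. It hides a between-arm difference fully when only dipstick positivity differs, and dilutes it otherwise (ratios of 1.01 to 1.18 in place of 1.35 to 1.57 in Case 2). All these rates are assumptions; the SAP supplies only the arm size. The selection itself and the cancellation of d do not depend on them.

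The consequence is bounded: counts, n and N remain on the page, and urinary infection has its own adverse event summary. This is a correction worth making to a descriptive safety table. It does not threaten the trial's safety conclusions as a whole.

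**What to change.** Amend SAP 9.4 as follows.

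1. For white cells, red cells or blood, bacteria and any culture summary, report the number abnormal as a percentage of Safety Set patients attending the visit. Patients dipsticked is an acceptable alternative at Week 4, Week 12 and Follow-up, where the dipstick is scheduled for everyone attending. State that the figure is abnormality detected by dipstick followed by central test, so that it is not mistaken for imputation of unmeasured values under Section 5.4.
2. Show the number and percentage dipstick-positive by arm and visit. Use site dipstick results if they are in the database, with an exemption from the central-laboratory-only rule. The SAP does not say whether they are; if not, use the number with a central urinalysis.
3. Do not count dipstick-negative patients as normal for glucose, protein, pH, specific gravity or color. Label those summaries, and every Week 8 urinalysis summary, as limited to the selected patients tested.
4. Note at Follow-up that patients who enter the extension study do not have this visit (Section 3.6 and schedule footnote 26), so its percentages describe those who attend.

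The cost is SAP wording and one changed table shell, with no new procedure. The small downside is that site-read dipstick results may enter a table.
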